Treatment Failure Event. Treatment failure event is defined as death, graft failure, or grade 3-4 toxicity secondary to CTL infusion in 6 months after CTL infusion. The Bayesian method of Thall, et al. will be used to monitor non-relapse mortality (regimen-related death, RRD). Assume that $T \sim \text{exponential}$ with median m , and that *a priori* $m \sim \text{inverse gamma}(3, 13.9)$, which has mean 6.96, corresponding to historical probability $\text{Pr}(T < 6 \text{ months}) = 0.45$. The trial will be stopped early if $\text{Pr}(m > 6.96 \text{ months} \mid \text{data}) < 0.0717$. In terms of median of T , the early stopping event is $[m > 6.96 \text{ months}]$, which is equivalent to $[\text{mean}(T) > 10.04 \text{ months}]$ because T follows an exponential distribution.

Early Deaths. If a patient treated for CMV dies from any cause before day 28, or drops out for some reason, that will be counted as a failure when scoring 28-day success. Due to the lack of computer software to jointly model the two different types of death, regimen-related and not regimen-related, which are competing risks, and non-fatal 28-day failure, and implement a design which separates these events, if a death within 28-days is regimen-related, then the design will "double count" the event. Specifically, such a death will be scored as an event in the monitoring rule for m and also as a 28-day failure in the monitoring rule for p . Consequently, the monitoring rules are conservative. It is anticipated, however, that the actual probability of such very early deaths will be very small, so these considerations will not substantively affect trial conduct.

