Operating Characteristics. The design's operating characteristics, with these two early stopping rules both implemented, are given below in Table 7. Due to the lack of computer software to evaluate the two monitoring rules together, (i) it is not possible to obtain achieved sample size distributions, and moreover (ii) it was necessary to compute the overall early stopping probability, given in the last column of Table 1, under the simplifying assumption that p and m are independent parameters, which of course is not true. However, denoting $Sp = [\text{stop due to the rule for } p]$ and $Sm = [\text{stop due to the rule for } m]$, since $\text{Pr}(Sp) = \text{Pr}(Sp | Sm)\text{Pr}(Sm) + \text{Pr}(Sp | \text{not } Sm)(1 - \text{Pr}(Sm))$, if p and m are positively associated, which seems a reasonable assumption, then $\text{Pr}(Sp | Sm) > \text{Pr}(Sp)$ and $\text{Pr}(Sp | \text{not } Sm) < \text{Pr}(Sp)$, so it is unclear precisely how actual association between the two parameters will affect the joint behavior of the two rules. If appropriate computer software were available, this issue could be explored more precisely.

Secondary Outcomes. Additional outcomes will include overall survival time, disease-free survival time, relapse rate, secondary graft failure, and graft-versus-host disease as an ordinal outcome. Each of these variables which will be analyzed as a function of patient covariates using standard statistical methods, including Bayesian survival regression analysis and ordinal regression. Unadjusted event time distributions will be estimated using the Kaplan-Meier method.

Table 7. Operating characteristics of the two early stopping rules.

Scenario	P(Response)	P(Death < 6 Months)	P(Stop Early due to Response Rule)	P(Stop Early due to Death Rule)	P(Stop Early: Overall)
1	0.50	0.45	0.070	0.100	0.163
2	0.30	0.45	0.681	0.100	0.712
3	0.50	0.60	0.070	0.374	0.418
4	0.30	0.60	0.681	0.374	0.800
5	0.50	0.65	0.070	0.648	0.672
6	0.30	0.65	0.681	0.648	0.888

Stopping Rules

The Bayesian decision cut-off for the treatment failure time event is to **STOP** accrual to the trial if $\text{Prob}(\text{median} > 6.96 | \text{data}) < 0.0717$.

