The following examples illustrate how this rule behaves with actual data. The key points in understanding the rule are that (1) each patient's data consist of either the time of the failure event if it occurred, or the patient's current following time if the event has not occurred and (2) all of the information needed by the rule is summarized by two statistics:

Nevents = the total number of events that have occurred

TFU = total follow up time

In general,

- 1) for given Nevents, larger TFU gives a smaller $\text{Prob}(\text{median} > 6.96 | \text{data})$
- 2) for given TFU, larger Nevents gives a smaller $\text{Prob}(\text{median} > 6.96 | \text{data})$

Example 1.

patient 1: event at 20 days

patient 2: followed for 100 days, no event

patient 3: event at 25 days

patient 4: event at 25 days

Nevents = 3, TFU = 170 \rightarrow $\text{Prob}(\text{median} > 6.96 | \text{data}) = 0.066$

Since this is smaller than the fixed decision cut-off .0717, the decision is **STOP**.

Example 2.

patient 1: event at 30 days

patient 2: followed for 100 days, no event

patient 3: event at 50 days

patient 4: event at 40 days

Nevents = 3, TFU = 220 \rightarrow $\text{Prob}(\text{median} > 6.96 | \text{data}) = 0.089$

Since this is larger than the fixed decision cut-off .0717, the decision is **DO NOT STOP**.

Example 3.

patient 1: event at 20 days

patient 2: followed for 100 days, no event

patient 3: followed for 70 days, no event

patient 4: event at 40 days

patient 5: event at 15 days

patient 6: followed for 40 days, no event

patient 7: event at 20 days

Nevents = 4, TFU = 305 \rightarrow $\text{Prob}(\text{median} > 6.96 | \text{data}) = 0.062$

Since this is smaller than the fixed decision cut-off .0717, the decision is **STOP**.

Data Safety Monitoring Board / DSMB at MDACC:

Select the name of the data safety monitoring board (DSMB) monitoring this protocol:
Not Applicable

Please explain:

This study is not randomized nor blinded.

Protocol Monitoring:

Does this protocol have a schedule for interim and final analysis? No

Provide a rationale for no interim analysis.

This study will be continuously monitored per the statistical design.

Protocol Monitoring Plan:

This study will be monitored by the MD Anderson IND Office and a protocol-specific monitoring plan will be followed.

Intellectual Property:

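### The failure event has a 6-month window but the follow-up entering the stopping rule has none stated; read together, late event-free time lowers the chance of stopping

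*Combined protocol and SAP*

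**What the plan says.** Under Statistical Models and Early Stopping Rules, the Treatment Failure Event paragraph states: "Treatment failure event is defined as death, graft failure, or grade 3-4 toxicity secondary to CTL infusion in 6 months after CTL infusion". The Stopping Rules section ties the 0.0717 threshold to that event: "The Bayesian decision cut-off for the treatment failure time event is to" stop accrual when the posterior probability that the median exceeds 6.96 months falls below it.

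The key points before the worked examples say that each patient enters with the failure time, "or the patient's current following time if the event has not occurred". They add that "all of the information needed by the rule is summarized by two statistics": the number of events, and "TFU = total follow up time". No section truncates that follow-up at 6 months. The model is a plain exponential; the plan converts the median to a mean "because T follows an exponential distribution".

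Other text describes the monitored quantity differently. Treatment and Primary Outcomes makes time to non-relapse mortality a primary endpoint. The paragraph on the Clinical Trial Conduct website says that this time is what will be monitored. The sentence directly after the failure-event definition also says the method monitors non-relapse mortality. None of these three statements carries a 6-month limit.

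**The concern.** An exponential likelihood estimates a rate as events divided by time at risk, so both must cover the same period. If a failure can count only up to month 6, a patient who passes month 6 without one is no longer at risk of a countable event. Under the stated definition of total follow-up (TFU) that patient still adds time as if at risk. The extra time lowers the apparent failure rate and raises the posterior probability that the median exceeds 6.96 months, which moves the rule away from stopping.

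The planned timetable leaves room for this. Infusing 36 patients at 2 per month takes about 18 months, so the earliest patients could each carry up to 18 − 6 = 12 months in which nothing can count. The longest follow-up in the worked examples is 100 days, so they do not show how later time is handled. At stake is the stopping probability that Table 7 gives for the rule on death, graft failure and severe toxicity.

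**Working it through.** **Inputs.** The prior on the median is inverse gamma(3, 13.9), the reference median is 6.96 months and the cut-off is 0.0717 (Treatment Failure Event; Stopping Rules). The maximum is 36 infused at about 2 per month (Treatment and Primary Outcomes). The six-month failure rates are those of Table 7: 0.45, 0.60 and 0.65.

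**Reproducing the plan's posterior.** With N events and TFU in 30-day months, Pr(m > 6.96 | data) = P(3 + N, (13.9 + c × TFU)/6.96), where P is the regularised lower incomplete gamma function.

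| N, TFU (days) | Plan | c = 1 | c = ln 2 |
|---|---|---|---|
| 3, 170 | 0.066 | 0.0661 | 0.046 |
| 3, 220 | 0.089 | 0.0891 | 0.059 |
| 4, 305 | 0.062 | 0.0621 | 0.034 |

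Only c = 1 matches, so it is the plan's coding in practice and leads below. A true median would need the ln 2 factor; that is a separate inconsistency.

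**Direction.** The Stopping Rules section says that more follow-up lowers the probability. Its own Examples 1 and 2 show the reverse: at 3 events, going from 170 to 220 days raises it from 0.066 to 0.089. The formula agrees with the examples.

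**A snapshot (c = 1).** Take 10 events at a mean of 1.5 months (15 months in total) and 4 event-free patients. The rule stops at 10 events if TFU is below 42.9 months.

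- Time credited to 6 months: TFU = 15 + 24 = 39, probability 0.0465, stop.
- Time credited to 9 months: TFU = 15 + 36 = 51, probability 0.149, do not stop.
- Time credited to 12 months: TFU = 15 + 48 = 63, probability 0.317, do not stop.

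The failures are identical in all three cases.

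**Simulation (c = 1).** Assumptions: 36 patients; Poisson entry at 2 per month; exponential failure times with monthly hazard −ln(1 − p)/6, that is 0.0996, 0.1527 and 0.1750; the rule checked every 0.1 month until the last entry; 20,000 trials.

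| Six-month rate | Table 7 | Events and TFU both unlimited | Events to 6 months, TFU capped | Events to 6 months, TFU uncapped |
|---|---|---|---|---|
| 0.45 | 0.100 | 0.075 | 0.076 | 0.068 |
| 0.60 | 0.374 | 0.391 | 0.366 | 0.276 |
| 0.65 | 0.648 | 0.597 | 0.553 | 0.410 |

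The loss from not capping is 0.008, 0.090 and 0.143. Separate runs, varying the checking schedule and whether patients who fail after month 6 go on adding time, put the uncapped figures at 0.28 to 0.30 (60%) and 0.41 to 0.44 (65%). No version reproduces the whole Table 7 column.

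**Sensitivity to accrual (c = 1).** At 1 infusion per month the fall is larger: 0.396 to 0.226 at 60% and 0.585 to 0.326 at 65% (3,000 trials). At 5 per month it is about 1 point or less while accrual continues.

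**When stops are lost (c = 1).** Mean numbers infused rise from 28.0 to 29.0 at 60% and from 24.2 to 25.8 at 65%. In a 6,000-trial run, the probability of having stopped by the 18th infusion barely moves: 0.279 capped against 0.263 uncapped at 60%, and 0.395 against 0.372 at 65%. Most of the loss therefore comes later.

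**With ln 2.** Capped: 0.278, 0.797 and 0.913. Uncapped: 0.204, 0.611 and 0.764. The direction is the same.

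**The case against.** The strongest objection is that the text does not establish that a death in month 8 is uncounted. The 6-month phrase comes last in the definition and may qualify only toxicity, and the monitored time is elsewhere non-relapse mortality without limit. If late deaths count, late exposure is legitimate for them and most of the effect disappears. This stands, and it is why the size above is conditional. It does not remove the problem: the analyst running the rule still cannot tell whether such a death is an event.

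A second objection runs the other way. Graft failure is monitored for the first 6 months after infusion and correlative sampling ends at 6 months, so current follow-up might mean time inside the window. That is possible, but the plan does not say so.

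Third, both versions with matching windows lie closer to Table 7 than the mismatched one. This suggests that the design was evaluated with matching windows and that the fault lies in the wording. It is not proof, since no version fits the column.

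A reader might infer that the safety rule simply stops too rarely, or that it is the trial's only protection. The documents support neither. Under the ln 2 coding even the uncapped rule stops more often than Table 7 states (0.611 against 0.374 at 60%). Any death before day 28 also counts as a failure in the response rule, and the first three patients are observed for 28 days before further enrolment.

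**Conclusion.** The point holds as an unreconciled mismatch between the event window and the exposure window. If the 6-month limit covers all components, the literal rule lowers the probability of stopping by roughly 0.07 to 0.09 at a 60% failure rate and 0.11 to 0.14 at 65%, and by at most about 0.01 at the historical 45%. These figures rest on the worked-example coding, exponential failure times and 2 infusions per month. They shrink to about a point or less at 5 per month and grow at 1 per month. The cost falls late in accrual and averages about one to one and a half extra patients infused. If deaths after month 6 are meant to count, the fault is the event definition, and most of this loss does not arise. The documents do not show which was intended.

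**What to change.** Make the two windows match, in one of two ways:

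- Define each patient's contribution to TFU as the time from infusion to the event, last follow-up or 6 months, whichever comes first.
- Remove the 6-month limit from the failure-event definition, so that later events count alongside later follow-up.

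Whichever is chosen, use the same description of the monitored event in the endpoint, website-monitoring and stopping-rule text. Then re-run the death-rule column of Table 7 and the overall column derived from it.

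The cost is one sentence, for the first option a cap in the monitoring program, and a re-run. The cap raises stopping at the 45% rate by at most about 0.01 under the plan's coding. If the ln 2 factor is introduced, the cap raises it from about 0.20–0.21 to 0.27–0.28, against 0.100 in Table 7, so the 0.0717 cut-off would need rechecking in that case.

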6. The first three patients on protocol will be observed for at least 28 days for safety monitoring before more patients are enrolled in the study.

Supportive care

1. All patients should receive supportive care as clinically indicated.
2. It is essential to avoid steroid as those may interfere with the efficacy of the infused CMV-specific CTLs.
3. Steroids will be given only if the patient develops a severe or life-threatening reaction to the infused CMV-specific CTLs.

Initiation of anti-viral therapy

1. CMV viral load will be monitored at least weekly by PCR within the 28 days of autologous recipient-derived CMV-specific CTL infusion.

2. Indication to initiate anti-viral therapy will be determined by their response status as described in Table 4.

Table 4. Time-table for monitoring efficacy and initiation of anti-viral drugs

Monitoring	Day 5-7	Day 12-14	Day 19-21	Day 26-28
CMV DNA increase > 50% compared with baseline	X	X	X	X
CMV DNA \geq 5000 copies/ml	X	X	X	X
CMV DNA decrease < 50% compared with baseline			X	
CMV end-organ disease	X	X	X	X
X, indication to start anti-viral therapy				

Management of potential treatment toxicity

1. Microbial contamination of T-cell product.

There is a potential that processing the T-cell product will inadvertently introduce microorganisms that could cause infection in the recipient after the cells are infused. Cultures of the T-cell product will be obtained to monitor for contamination. In the event that a microbial contamination is discovered after infusion of CTLs, standard GMP procedures will be followed.

2. Graft failure: Graft failure is initial neutrophil engraftment followed by subsequent decline in the ANC to $< 500/\text{mm}^3$ for three consecutive measurements on different days, unresponsive to growth factor therapy that persists for at least 14 days in the absence of a known cause such as relapse. GF will be monitored as clinically indicated for the first 6 months after CTL infusion.

3. Graft Versus Host Disease (GVHD)

The risk of GVHD following the infusion of recipient-derived autologous CTLs is expected to be low.

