Management of Toxicity. CTLs are susceptible to killing by steroids give at a dose of 1-2 mg/kg. This is standard therapy for GVHD and could also be given if a recipient develops other complications considered possibly related to CTL administration. In the case of GF, second allogeneic HSCT from the same donor or other is the only effective treatment. Other supportive care would be per standard medical practice.

Table 6. Definite and Possible Manifestations of Chronic GVHD

Organ System	Definite manifestations of chronic GVHD	Possible manifestations of chronic GVHD
Skin	Scleroderma (superficial or fasciitis), lichen planus, vitiligo, scarring alopecia, hyperkeratosis pilaris, contractures from skin immobility, nail bed dysplasia	Eczematoid rash, dry skin, maculopapular rash, hyperpigmentation, hair loss
Mucous membranes	Lichen planus, non-infectious ulcers, corneal erosions/non-infectious conjunctivitis	Xerostomia, keratoconjunctivitis sicca
GI tract	Esophageal strictures, steatorrhea	Anorexia, malabsorption, weight loss, diarrhea, abdominal pain
Liver	None	Elevation of alkaline phosphatase, transaminitis, cholangitis, hyperbilirubinemia
GU	Vaginal stricture, lichen planus	Non-infectious vaginitis, vaginal atrophy
Musculoskeletal/ Serosa	Non-septic arthritis, myositis, myasthenia, polyserositis, contractures from joint immobilization	Arthralgia
Hematologic	None	Thrombocytopenia, eosinophilia, autoimmune cytopenias
Lung	Bronchiolitis obliterans	Bronchiolitis obliterans with organizing pneumonia, interstitial pneumonitis

Correlative Studies

40 to 60 mL of blood will be taken pre-infusion, then 2 weeks, 4 weeks, 3 months, and 6 months post-infusion to measure CMV-specific T-cell frequencies, immunologic analysis, general immune reconstitution, and persistence of adoptively infused autologous CMV CTLs.

Study Enrollment:

The study population for this research will consist of participants from:

Only at MDACC

Estimated Accrual:

Total Accrual at MDACC:	105
Estimated monthly accrual at MDACC:	2

Accrual Comments:

Due to the randomness of the treatable CMV subsample size, which is binomial in $q = .40$ and $n =$ number of patients initially enrolled and transplanted, up to 105 patients will be enrolled (21 months accrual) to ensure at least a 90% probability that there will be at least 36 patients with CMV.

Is this an NCI-Cancer Therapy Evaluation Protocol (CTEP)? No

Is this an NCI-Division of Cancer Prevention Protocol (DCP)? No

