Statistical Considerations:

Treatment and Primary Outcomes. This is a single-arm phase II trial of autologous virus specific CTLs for CMV reactivation in patients with hematologic malignancies (excluding T cell leukemia and lymphoma) undergoing CMV seronegative matched unrelated donor (MUD), mismatched unrelated or cord blood allogeneic stem cell transplant. Whole blood will be collected and frozen prior to transplant. After documentation of CMV reactivation, defined as CMV at a level ≥ 137 DNA copies/ml by PCR, autologous CMV-specific CTLs will be generated to be infused within 72 hours of CMV reactivation, if the patient has ANC engraftment, no acute GVHD or steroid administration ≤ 0.5 mg/kg dose. All outcomes will be recorded starting from the time of T-cell administration. While the dose of T-cells will vary depending on how many cells can be grown by ex vivo expansion after thawing and prior to administration, the maximum dose will be $10e5$ viable CD3+ T cells/kg. It is anticipated that 20-25 patients per year will be accrued and that approximately 2 patients per month will develop CMV reactivation and thus be eligible to receive autologous CTLs. A maximum of 36 patients will receive autologous CTLs. The two primary endpoints, starting at the time of autologous T-cell administration, will be $T =$ time to non-relapse mortality and $Y =$ [28-day success], where "success" is defined as follows. CMV will be evaluated weekly at 7, 14, 21 and 28 days using PCR. Treatment will be considered a success if the patient does not require initiation of CMV anti-viral therapy. Anti-viral therapy will be started if 1) End-organ disease is documented at any time point after CTL administration 2) Increase in CMV DNAemia $>50\%$ compared with baseline at any time point 3) Decrease in CMV DNAemia $<50\%$ compared with baseline at day 21 after CTL administration and 4) CMV DNAemia >5000 copies/ml at any time point.

Non-relapse mortality is defined as death because of causes other than relapse of the underlying hematological malignancy. Relapse of underlying hematological malignancy will be a competing event for non-relapse mortality. Time to non-relapse mortality is defined as time to non-relapse mortality from date

of stem cell transplantation.

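### The only safety stopping rule is calibrated to a 45% six-month event rate, and CTL-attributable graft failure and grade 3-4 toxicity have no limit of their own

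*Combined protocol and SAP*

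**What the plan says.** Under Statistical Models and Early Stopping Rules, the Treatment Failure Event paragraph opens with a composite: "Treatment failure event is defined as death, graft failure, or grade 3-4 toxicity secondary to CTL infusion in 6 months after CTL infusion". The next sentence says that the Bayesian time-to-event method "will be used to monitor non-relapse mortality (regimen-related death, RRD". The Clinical Trial Conduct website paragraph also names non-relapse mortality, Table 7 labels the rate as death within 6 months, and the Stopping Rules section returns to treatment failure.

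Whichever event is meant, the rule is the same. The event time is exponential with median m, and m has an inverse gamma prior with parameters 3 and 13.9. The reference median of 6.96 months is tied to a historical six-month probability of 0.45. Accrual stops when the posterior probability that m exceeds 6.96 falls below 0.0717. On exposure, the plan says "A maximum of 36 patients will receive autologous CTLs".

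On graft failure, Management of Toxicity says "In the case of GF, second allogeneic HSCT from the same donor or other is the only effective treatment", and the item on graft failure under Management of potential treatment toxicity says "GF will be monitored as clinically indicated for the first 6 months after CTL infusion".

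The other safeguards are:
- a stopping rule on 28-day success, which scores need for antiviral therapy, early death and dropout;
- a 28-day observation of the first three patients, with no stated criterion;
- monitoring by the institution's IND Office under a protocol-specific plan.

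The DSMB entry is Not Applicable.

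**The concern.** Secondary graft failure and CTL-related grade 3-4 toxicity are the events that the plan itself would attribute to the infused product. The only rule that could count them either pools them with all deaths and judges the total against 45%, or does not count them if non-fatal. A product-caused rate well below 45% could still matter, particularly where the plan says that graft failure can be treated only by another transplant. Table 7 shows no event rate below 0.45, so a reader cannot see how the rule behaves there. Safety of the CTLs is secondary objective 1, and the stated reason for having no interim analysis is that the design monitors continuously. The sensitivity of that monitoring to product-caused harm therefore matters.

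**Working it through.** **Inputs from the plan.** Prior inverse gamma(3, 13.9); reference median 6.96 months; cut-off 0.0717; at most 36 infusions; about 2 per month.

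**Assumptions.** A 20% six-month rate of CTL-attributable events; three timing patterns; background deaths of 0%, 20% or 45% at six months.

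**Formula.** With N events and total follow-up TFU in months, the posterior of m is inverse gamma(3 + N, 13.9 + k × TFU). So Pr(m > 6.96 | data) is the Gamma(shape 3 + N) distribution function at (13.9 + k × TFU)/6.96. If m is a median, as the text says, k = ln 2. The worked examples fit only k = 1, so both are carried through.

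**Reproducing the plan's figures.**
- Anchor: 1 − 2^(−6/6.96) = 0.450, as stated. Prior mean: 13.9/2 = 6.95.
- Worked examples, 30-day months: k = 1 gives 0.066, 0.089 and 0.062, as printed; k = ln 2 gives 0.046, 0.059 and 0.034.
- Table 7 response column: 0.070 and 0.681 reproduce by exact recursion.
- Table 7 death column (0.100 / 0.374 / 0.648): k = 1 gives about 0.07-0.08 / 0.39-0.44 / 0.60-0.66, close but not exact; k = ln 2 gives about 0.33 / 0.93 / 0.99. The plan does not give its simulation settings.

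**What 20% looks like to the rule.** The expected count is 0.20 × 36 = 7.2. Take 7 events at one month and 29 patients followed for 6 months: TFU = 7 + 174 = 181.
- k = 1: (13.9 + 181)/6.96 = 28.0, posterior above 0.999.
- k = ln 2: (13.9 + 125.5)/6.96 = 20.0, posterior 0.995.

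Both are far above 0.0717. With all 36 fully followed, stopping needs 21-27 events (k = 1) or 18-21 (k = ln 2), for mean event times of 0.5 to 3 months.

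**Simulated chance of stopping, composite reading** (36 infusions at 2 per month, checked at each event; ranges run from k = 1 to k = ln 2, and follow-up convention and simulation error move most values by about a point):

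| 20% CTL events | Background deaths | Chance of stopping |
|---|---|---|
| Constant hazard | none | 0.3-1% |
| Days 14-60 | none | 3-7% |
| All in month 1 | none | 9-17% |
| Constant hazard | 20% | 3-11% |
| Constant hazard | 45% | about 26% (k = 1); 67% or more (k = ln 2) |

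In the last row the composite rate is 1 − 0.80 × 0.55 = 0.56. Linear interpolation in Table 7 gives 0.100 + (0.11/0.15) × 0.274 = 0.30, consistent with the k = 1 figure.

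**Non-relapse-mortality reading.** A non-fatal graft failure or toxicity adds nothing to N, so it cannot trigger the rule at any rate.

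**First three patients.** Suppose two have events on days 20 and 25 and the third is event-free at day 28: N = 2, TFU = 73 days. The posterior is 0.077 (k = ln 2) or 0.089 (k = 1), so the trial continues. This depends on follow-up: with two events, the stated median rule stops when TFU is about 58 days or less (about 40 for k = 1). If the third patient had only 13 days, TFU would be 45 + 13 = 58 and the stated rule would stop.

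**The case against.** A reader might infer that the rule would almost never stop the trial at a 20% CTL-event rate, or that nothing in the plan reacts to such harm. The documents do not support either statement without conditions. On the composite reading deaths count in the same total, and the plan's own reference is 45%. On top of 45% deaths the rule stops in about a quarter of trials or more. Early clustering also helps, because events then fall on short follow-up: 9-17% if all occur in month 1. That pattern suits acute toxicity better than graft failure, which by the plan's definition must persist for at least 14 days.

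Other oversight also exists. The IND Office follows a monitoring plan that is not in these documents, and enrolment is held after the first three patients. It would be wrong to say that all 36 would necessarily be infused. The plan also gives neither an expected CTL-event rate nor a tolerable one, so 20% is only a scenario.

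These objections limit the wording, not the point. Neither the three-patient hold nor the monitoring statement gives a numerical criterion. Where stopping becomes likely, background deaths supply much of the signal, so a stop would not tell the investigators that the product was responsible. Low mortality, otherwise good news, leaves the rule least sensitive to graft loss.

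**Conclusion.** The point holds with conditions. The only safety rule is calibrated to a 45% six-month event rate and sets no separate limit for CTL-attributable graft failure or grade 3-4 toxicity. On the composite reading, at a 20% rate with few other events, it stops 0.3-1% of trials under the design's own constant-hazard model, 3-7% with events on days 14-60 and 9-17% with all events in month 1. The chance rises materially only with background deaths. On the non-relapse-mortality reading, non-fatal harm never counts.

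The sizes rest on the assumed 20% rate, the assumed timing and 2 infusions per month, and they span both versions of the formula. The stronger inference, that the trial has no working safety stop, does not follow on the composite reading. The three-patient example illustrates the rule but depends on follow-up at the moment of checking. This is a design weakness that should be corrected; it does not show that the trial would be unsafe.

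**What to change.** 1. State which event the time-to-event rule monitors, and make the Treatment Failure Event paragraph, the website paragraph, the Stopping Rules section and Table 7 agree.
2. Keep that rule for mortality.
3. Add a separate beta-binomial boundary, in the same Bayesian style as the 28-day success rule, for CTL-attributable graft failure or grade 3-4 toxicity. The investigators set the tolerable rate, prior and cut-off.
4. Check the boundary at the review of the first three patients, and add its operating characteristics to Table 7 at event rates below 45%.

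The cost is one paragraph and one boundary table, with no extra patients or visits, plus a small added false-stop probability. As an illustration of scale only, not a proposal: a limit of 0.10, a beta(0.5, 4.5) prior and a 0.95 cut-off stop 60% of trials at a true 20% rate and 94% at 30%, against 1% at 5% and about 10% at 10%. These settings would not stop at 2 events in 3 patients: the posterior is beta(2.5, 5.5), and Pr(rate > 0.10) = 0.934 is below 0.95. If the investigators want the three-patient review to act on that result, they must choose settings that do so and accept the corresponding false-stop rate.
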